If this application involves the use of a HUD “humanitarian” device: describe whether the use is for “on-label” clinical patient care, “off-label” clinical patient care, and/or research (collecting safety and/or effectiveness data).

Patients with hyperglycemia have heterogeneous physiologies and their insulin requirements are highly varied. The currently available algorithms cannot precisely predict their initial insulin doses. More importantly, there is no algorithm so far that is supported by evidence.

We hypothesize that standardized algorithms using multiple factors can more precisely predict patients' individual insulin requirements on hospital admission. Our prospective study (STUDY00015475) at the University of Washington (UW) built an insulin calculator for patients with T2DM on home insulin and adequate oral intake peri-admission (sample size 140). Using multivariable regression models, our predicted daily insulin doses have a correlation factor of 0.793 with their actual insulin requirements. No outlier that would be severely overdosed was noted in our observational cohort.

The factors used to predict insulin requirement are patients' oral intake plan, home insulin dose, first blood glucose value on presentation, inpatient glucocorticoid dose, systemic inflammatory response syndrome (SIRS), dose and timing of last long-acting insulin prior to admission. Our online calculator (<https://inpatientinsulin.com>) will be used to calculate the initial insulin dosing regimen.

Our calculator is based on observational studies, so it remains unclear whether it can help clinicians achieve recommended glycemic targets. We propose using these calculators can achieve inpatient glycemic goal of 100-180 mg/dL (American Diabetes Association's guidelines 2023) faster than the standard of care with less manual adjustments. Before we perform a study of a large sample size, it is important to test whether using this calculator in the clinical setting is safe. This study is a feasibility trial to mainly investigate its safety (no excessive hypoglycemia). We will also examine whether using this calculator decreases hyperglycemia. The trial will provide opportunities to adjust the algorithms before the randomized controlled trial.

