It is not necessary to summarize all the discussion that has led to the development of the study protocol. The IRB is interested only in short summaries about experiences or preliminary work that suggest the study is feasible and that risks are reasonable relative to the benefits. Examples: Your team has already conducted a Phase 1 study of an experimental drug which supports the Phase 2 study being proposed in this application; your team has already done a small pilot study showing that the reading skills intervention described in this application is feasible in an after-school program with classroom aides; your team has experience with the type of surgery that is required to implant the study device; the study coordinator is experienced in working with subjects who have significant cognitive impairment.

Our proof-of-concept study at UC Davis identified several factors associated with initial insulin requirements for patients with history of diabetes mellitus (DM) and any BG value ≥ 180 mg/dL during the first 24 hours of hospitalization [1]. Then our prospective study at the University of Washington (UW) built insulin calculators for patients with different types of DM. For the study population of this trial, patients with T2DM or steroid-induced DM who take insulin prior to admission, our predicted daily insulin dose has a correlation factor of 0.795 with their actual insulin requirements. In addition, we excluded outliers (who have low oral intake before or after admission) so the rest of patients show no severe overdose in our cohort.

1. [name] HH, Surampudi P, Sood A. Determinants of initial insulin therapy for hospitalized patients with diabetes mellitus. J Diabetes Complications. 2022 Oct;36(10):108307.

1.8.c. Subject matter expertise. Is the study a clinical trial and/or does the study involve use of a drug, biologic, botanical, nutritional supplement and/or is the study otherwise considered to be greater than minimal risk to subjects?

- ☐ **No** → Answering this question is optional.
- ☒ **Yes** → Provide the name, degree(s), and contact information (e.g., email, phone number) of someone with appropriate expertise in the subject matter described in the objectives and design of this study. The individual should be unaffiliated with the study and have no other apparent conflict of interest. The individual may be associated with the UW or external to the University. Ensure the individual is aware they may be contacted by HSD.

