2. PARTICIPANTS

2.1. [DETERMINATION] Participants. Describe the general characteristics of the subject populations or groups, including age range, gender, health status, and any other relevant characteristics.

Document Date & Version

06.29.2023

Version 4.6

APPLICATION IRB Protocol

Researcher Date & Version

mm/dd/yyyy

Version x.x

Page 7 of 55

We plan to recruit adult patients who are admitted to UW Montlake, Harborview and Northwest hospitals with history of type 2 diabetes mellitus on insulin therapy prior to admission. Because we work with the internal medicine hospitalist group, these patients are admitted for various non-critical acute illnesses from the emergency room. They can also be non-emergent admissions from the clinics. The obstetrics ward tends to use a different glycemic goal than other inpatient populations, so we exclude patients admitted to obstetrics ward. Our prior observation cohort did not include patients admitted for elective surgery or procedure, so our calculator has not been validated in this population.

2.2. [DETERMINATION] Inclusion and exclusion criteria.

2.2.a. Inclusion criteria. Describe the specific criteria that will be used to decide who will be included in the research from among interested or potential subjects. Define any technical terms in lay language.

1. Patients who are admitted to University of Washington Medical Center – Montlake, Harborview and Northwest hospitals
2. Aged ≥ 18 years
3. With history of type 2 or steroid-induced diabetes mellitus
4. Receiving insulin therapy prior to admission

2.2.b. Exclusion criteria. Describe the specific criteria that will be used to decide which of the subjects who meet the inclusion criteria listed above will be excluded from the research. Define any technical terms in lay language.

1. Patients who are admitted to ICU or obstetrics ward
2. Patients who are admitted for elective surgery or procedure
3. Patients who present with diabetic ketone acidosis, hyperosmolar hyperglycemic state or need IV insulin infusion
4. Patients who have no meal intake for 24 hours prior to admission, planned nothing per oral (NPO) during the first 24 hours after admission
5. Patients who report low appetite (25% or less) on admission or have a significantly decreased level of consciousness that study team does not think they are going to eat right after admission
6. Patients who receive enteral feeding after admission

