This consent process will be part of the admission interview which happens either in the emergency room or hospital room. If subjects are not able to consent, the hospitalists will obtain consent from their legally authorized representatives' (LAR) in person or on the phone.

Patients who report low appetite 25% or less, NPO for 24 hours before admission, or planned NPO for 24 hours after admission will be excluded because they have risk to be overdosed by our predicted insulin doses. If patients had a significantly decreased level of consciousness that the study team does not think they are going to eat right after admission, they will also be excluded from this trial.

Hospitalists that are going to enroll subjects will join a one-hour launch meeting when the PI will introduce the study procedure and how to use the online calculator. There will be a session of questions and answers. At the end of the meeting, we will assess whether the hospitalists feel comfortable to start enrolling patients. If they do not feel ready, we will plan further meetings before they start the enrollment.

Hospitalist Enrollment

If subjects agree to join this trial, hospitalists will go to our online calculator to calculate the initial insulin dosing regimen (<https://inpatientinsulin.com>). The questions in the online calculator will be asked during the interview with the subjects. Some information required in the calculator may be obtained from a caregiver rather than the subject if the caregiver knows the information better. In this case, the hospitalists will obtain consent from the subject or LAR before receiving health information from a caregiver. Hospitalists will confirm whether the caregiver knows the required information well, as the standard of care. If hospitalists could not obtain reliable information within 20% range (plus minus 10%), this subject will not be enrolled. For example, if a subject's home daily insulin dose cannot be confidently narrowed within the 36 - 44 units range, This subject will not be enrolled using home daily insulin dose of 40 units in the calculator.

Resident Enrollment

If patients are admitted to the teaching service (residents' service), attending hospitalists will obtain informed consents and calculate the initial insulin doses personally. Attending hospitalists will work with residents closely to do standard insulin adjustments. When changing shifts, attending hospitalists will sign out to the next attendings.

PI Enrollment

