We plan to extract data from the inpatient Electronic Medical Record (EMR), including demographic characteristics (age, gender, race, weight, height), diabetes history (diabetes type, home antidiabetic medications), vital signs, laboratory measurements (POC BG and laboratory venous BG, latest hemoglobin A1c, renal function), interventions (inpatient insulin dose and modality, glucocorticoid, pain medication, surgery or procedure), nutrition status (oral intake, tube feed, intravenous dextrose), and hospital admission/discharge dates.

Our UW observational cohort (STUDY00015475) has 1/140 patients (0.7%) who had hypoglycemia < 54 mg/dL during the first 24 hours of hospitalization. We think (and from prior inpatient glycemic trials) 3% increase (which means 3.7%) is considered clinically significant increase, so among these 85 subjects there cannot be more than $85 \times 3.7\% = 3.15$ subjects that develop hypoglycemia < 54 mg/dL. So, if we find more than 3.15 patients (round to 4) who develop BG < 54 during the recruitment, that is more than 3% increase. Because this is the first feasibility trial to apply the calculator on patients, we plan to enroll 10 subjects first, to demonstrate the calculator dose does not cause hypoglycemia (≤ 54 mg/dL). After these 10 participants are recruited, we will review and analyze these data. Then we will apply for a modification to increase the sample size.

To examine the feasibility, the specific outcomes that will be measured are hypoglycemia (< 54 mg/dL), mean BG during the first 24 hours of hospitalization, and hyperglycemia (≥ 300 mg/dL), compared to our UW observational cohort ([STUDY00015475](#)).

The International Hypoglycemia Study Group defined three levels of hypoglycemia for the purpose of standardized reporting: BG < 70 mg/dL (level 1), < 54 mg/dL (level 2), < 40 mg/dL (level 3) [1]. Centers for Medicare & Medicaid Services (CMS) use the same definition to capture hospital glycemic data [2]. BG < 54 mg/dL was defined as clinically significant hypoglycemia and used in prior inpatient glycemic trials [3].

For statistical analyses, trial subjects (single-arm study with utilization of the insulin calculator) will be compared with the UW observational cohort (STUDY00015475) where standard of care was used (mostly by physicians' experience). The primary endpoint is hypoglycemia < 54 mg/dL. The secondary endpoint is mean BG during the first 24 hours of hospitalization and hyperglycemia (≥ 300 mg/dL).

Reference

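### The hypoglycemia limit of 3.7% (3.15 events in 85) treats one event in 140 as an exact rate, and the cohort behind that rate is not shown to match the trial on oral intake

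*Combined protocol and SAP*

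**What the plan says.** Section 5.1, repeated in 10.1, sets the rule for the primary endpoint, hypoglycemia below 54 mg/dL. The benchmark is that the cohort "has 1/140 patients (0.7%) who had hypoglycemia < 54 mg/dL during the first 24 hours of hospitalization". A "3% increase (which means 3.7%) is considered clinically significant increase", and "among these 85 subjects there cannot be more than" 3.15 with an event; the section rounds this to 4. No interval or other allowance is attached to the 0.7%. Section 1.5 names a t test for mean glucose and a chi-squared test for hyperglycemia, but for hypoglycemia it gives only the 3-point limit.

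Section 1.5 describes the calculator's development cohort as "patients with T2DM on home insulin and adequate oral intake peri-admission (sample size 140"). Section 1.8.b says "we excluded outliers (who have low oral intake before or after admission) so the rest of patients show no severe overdose in our cohort".

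The trial also restricts on intake. Section 2.2.b excludes no meals in the 24 hours before admission, planned NPO for the 24 hours after, "Patients who report low appetite (25% or less) on admission", patients whom the study team does not expect to eat because of reduced consciousness, and enteral feeding after admission. Section 5.1 says that low-appetite and NPO patients "will be excluded because they have risk to be overdosed by our predicted insulin doses".

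**The concern.** The rule compares two groups but is built as if one of them were known without error. Section 5.1 says that trial subjects will be compared with the cohort, which calls for an estimate of the difference between two uncertain rates. Counting against a fixed 3.15 answers another question: whether the trial's observed rate is above 3.7%. With one cohort event and 85 trial subjects, both sides of the comparison are imprecise. Staying at 3 events or fewer could then be read as showing that the calculator adds less than 3 points of hypoglycemia, which the data could not support. Section 1.5 makes this safety question the main purpose of the trial, ahead of a randomized study.

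The second question is whether 1/140 describes the kind of patient being enrolled. If cohort patients were removed because of what they ate after admission, while the trial keeps subjects who were expected to eat and then did not, the two groups differ on a factor that the protocol itself links to overdose.

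**Working it through.** **1. The plan's figure.** Inputs from section 5.1: 1 event in 140, margin 3 points, N = 85.
- 1/140 = 0.714%; plus 3 points = 3.714%.
- 85 × 3.7% = 3.145 and 85 × 3.714% = 3.157. Both agree with the stated 3.15, and the first whole count above it is 4.

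**2. Precision of the benchmark.** Clopper-Pearson 95% limits for 1/140:
- Lower: 1 − 0.975^(1/140) = 0.018%.
- Upper: 97.5% quantile of Beta(2, 139) = 3.92%.
- A Wilson interval gives 0.13% to 3.93%.

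The upper limit is above the 3.7% limit itself.

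**3. Carrying that interval through the rule.**
- 85 × (0.00018 + 0.03) = 2.6.
- 85 × (0.0392 + 0.03) = 5.9.

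The first count above the limit could be anything from 3 to 6.

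**4. Behaviour of the 4-event count.** P(X ≥ 4) for X ~ Binomial(85, p):

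| True rate p | P(4 or more events) |
|---|---|
| 0.714% | 0.3% |
| 2% | 9% |
| 3% | 25% |
| 3.7% | 39% |
| 3.92% | 43% |
| 5% | 62% |

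At p = 3.7%, the probabilities of 0, 1, 2 and 3 events are 0.041, 0.133, 0.214 and 0.227. They sum to 0.614, so a calculator exactly at the limit stays below 4 events 61% of the time.

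**5. What a passing result would show.** Newcombe upper limit = d + √[(u₁ − p₁)² + (p₂ − l₂)²], where u₁ and l₂ are Wilson limits with z = 1.645 (one-sided 95%). For 3/85 against 1/140:
- p₁ = 3.53%, u₁ = 8.51%; p₂ = 0.71%, l₂ = 0.16%; d = 2.82 points.
- 2.82 + √(4.98² + 0.55²) = +7.8 points.

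| Trial events | Difference from cohort (points) | One-sided 95% upper limit (points) |
|---|---|---|
| 0/85 | −0.7 | +2.4 |
| 1/85 | +0.5 | +4.4 |
| 2/85 | +1.6 | +6.2 |
| 3/85 | +2.8 | +7.8 |

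Miettinen-Nurminen limits are nearly the same (+2.39, +4.45, +6.23, +7.87). Only 0/85 excludes a 3-point excess. If the calculator's true rate were exactly 1/140, P(0/85) = (139/140)^85 = 54%.

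**6. Intake selection, side by side.**
- *Cohort:* low intake before or after admission was removed (1.8.b). The development cohort of 140 had adequate intake around admission (1.5), and 5.1 uses the same denominator. So 1/140 is very probably the rate after the filter, though no section says so outright. Whether intake after admission was planned or observed is not defined.
- *Trial:* apart from enteral feeding, the intake criteria rest on history, report, plan or judgement at admission (2.2.b). The withdrawal rules in 10.8 cover IV insulin infusion, hospitalist discomfort with the dose after midnight, and insulin already given. None covers an enrolled subject who then eats poorly.

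**7. Size of a possible mismatch, by assumption only.** Suppose a share f of enrolled subjects eats poorly and has RR times the benchmark risk. The matched benchmark is then [(1 − f) + f × RR]/140.
- f = 10%, RR = 2: 1.1/140 = 0.8%; limit 3.8%; P(4 or more) with no calculator effect 0.5%.
- f = 30%, RR = 10: 3.7/140 = 2.6%; limit 5.6%; P(4 or more) with no calculator effect 19%.

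Neither f nor RR is given in the documents.

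**The case against.** The strongest reply is that this is a single-arm feasibility trial. Section 5.1 says openly that a control arm was left out because a powered hypoglycemia comparison needs too many subjects, and that a larger randomized study will follow. On that view the 4-event count is a screen, and turning it into a non-inferiority test would be out of proportion. This stands. Requiring an upper limit below 3 points would pass only 0/85, so a calculator identical to the cohort would fail about 46% of the time. It does not remove the need to state how uncertain the comparison is.

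A reader might also infer that the cohort was stripped of patients who ate poorly after their first dose, so that the comparison is demonstrably not like with like. The documents do not support that:
- Section 1.8.b does not say whether low intake after admission was planned or observed. Section 1.5 lists the oral intake plan among the calculator's factors, so a plan-based filter is possible.
- The 1.8.b sentence, and the reason given in 5.1 for the trial's exclusions, concern overdose by the calculator's predicted doses. The 1/140 is hypoglycemia observed under standard care.
- The trial excludes largely the same low-intake patients. The only possible gap is patients expected to eat who then did not, and its size is unknown.

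Finally, the 25% false-alarm figure needs a true standard-care rate of 3%. At that rate, 1 or fewer events in 140 has probability 7.5%, so it is a near-extreme case.

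**Conclusion.** The precision point is established from the plan's own numbers. The 0.7% is compatible with 0.02% to 3.9%, and the count equivalent to a 3-point margin with 2.6 to 5.9. The rule misses a true 3.7% rate 61% of the time, and 3/85 leaves room for an excess of 7.8 points, more than twice the stated margin. Having 3 or fewer events therefore cannot by itself support a statement that hypoglycemia is no more than 3 points above the cohort. These figures assume independent subjects, and the risk-difference limits take the two groups as comparable.

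The comparability point is narrower. The cohort appears to have been selected on intake both before and after admission, the trial screens at admission, and the documents do not define the cohort filter. Comparability is not shown; a mismatch is not shown either. A reader might infer that the filter hides harm. The likely direction is the reverse: a benchmark that is too low gives a stricter limit and more false alarms.

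**What to change.** 1. In 5.1 and 10.1, keep the 4-event count as a safety screen and describe it as such. Report the primary endpoint as the trial-minus-cohort risk difference with a Newcombe or Miettinen-Nurminen interval, used descriptively and not as a pass/fail test. State that a 3-point excess will not be called excluded unless the interval shows it.
2. State how low intake after admission was defined in STUDY00015475. From those data, give the benchmark under criteria 2.2.a and 2.2.b as knowable at admission, keeping patients who ate poorly afterwards. If appetite at admission was not recorded, give the rate with and without the after-admission intake filter. Restate 0.7%, 3.7% and 3.15 if they change.

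The natural moment is the modification request planned after the first 10 subjects. The cost is a re-analysis of the team's own earlier study and new wording in two sections; no extra subjects are needed and dosing is unaffected. The drawbacks are that the interval will be wide and that the stated limit may change.

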2. PARTICIPANTS

2.1. [DETERMINATION] Participants. Describe the general characteristics of the subject populations or groups, including age range, gender, health status, and any other relevant characteristics.

Document Date & Version

06.29.2023

Version 4.6

APPLICATION IRB Protocol

Researcher Date & Version

mm/dd/yyyy

Version x.x

Page 7 of 55

We plan to recruit adult patients who are admitted to UW Montlake, Harborview and Northwest hospitals with history of type 2 diabetes mellitus on insulin therapy prior to admission. Because we work with the internal medicine hospitalist group, these patients are admitted for various non-critical acute illnesses from the emergency room. They can also be non-emergent admissions from the clinics. The obstetrics ward tends to use a different glycemic goal than other inpatient populations, so we exclude patients admitted to obstetrics ward. Our prior observation cohort did not include patients admitted for elective surgery or procedure, so our calculator has not been validated in this population.

2.2. [DETERMINATION] Inclusion and exclusion criteria.

2.2.a. Inclusion criteria. Describe the specific criteria that will be used to decide who will be included in the research from among interested or potential subjects. Define any technical terms in lay language.

1. Patients who are admitted to University of Washington Medical Center – Montlake, Harborview and Northwest hospitals
2. Aged ≥ 18 years
3. With history of type 2 or steroid-induced diabetes mellitus
4. Receiving insulin therapy prior to admission

2.2.b. Exclusion criteria. Describe the specific criteria that will be used to decide which of the subjects who meet the inclusion criteria listed above will be excluded from the research. Define any technical terms in lay language.

1. Patients who are admitted to ICU or obstetrics ward
2. Patients who are admitted for elective surgery or procedure
3. Patients who present with diabetic ketone acidosis, hyperosmolar hyperglycemic state or need IV insulin infusion
4. Patients who have no meal intake for 24 hours prior to admission, planned nothing per oral (NPO) during the first 24 hours after admission
5. Patients who report low appetite (25% or less) on admission or have a significantly decreased level of consciousness that study team does not think they are going to eat right after admission
6. Patients who receive enteral feeding after admission
7. Patients who develop severe acute kidney injury needing dialysis therapy

2.3. [DETERMINATION] Prisoners. IRB approval is required in order to include prisoners in research, even when prisoners are not an intended target population.

Is the research likely to have subjects who become prisoners while participating in the study?

For example, a longitudinal study of youth with drug problems is likely to have subjects who will be prisoners at some point during the study.

☒ **No**

☐ **Yes** → If a subject becomes a prisoner while participating in the study, will any study procedures and/or data collection related to the subject be continued while the subject is a prisoner?

☐ **No**

☐ **Yes** → Describe the procedures and/or data collection that will continue with prisoner subjects.

Click or tap here to enter text.

2.4. [DETERMINATION] Will the proposed research recruit or obtain data from individuals that are known to be prisoners?

For records reviews: if the records do not indicate prisoner status and prisoners are not a target population, select “No”. Review the guidance on [Prisoners](#) for the definition of “prisoner”, which is not necessarily tied to the type of facility in which a person is residing.

☒ **No**

☐ **Yes** → Answer the following questions (**2.4.a. – 2.4.d.**)

2.4.a. Describe the type of prisoners, and their locations(s).

Click or tap here to enter text.

2.4.b. One concern about prisoner research is whether the effect of participation on prisoners’ general living conditions, medical care, quality of food, amenities, and/or opportunity for earnings in prison will be so great that it will make it difficult for prisoners to adequately consider the research risks. How will the chances of this be reduced?

Click or tap here to enter text.

2.4.c. Describe what will be done to make sure that (a) recruitment and subject selection procedures will be fair to all eligible prisoners and (b) prison authorities or other prisoners will not be able to arbitrarily prevent or require particular prisoners from participating.

Click or tap here to enter text.

2.4.d. If the research is funded by one of these federal departments and agencies (Health & Human Services; Energy; Defense; Homeland Security; CIA; Social Security Administration), and/or will involve prisoners in federal facilities or in state/local facilities outside of Washington State: check the box below to provide assurance that study team members will (a) not encourage or facilitate the use of a prisoner’s participation in the research to influence parole or pardon decisions, and (b) clearly inform each prisoner in advance (for example, in a consent form) that participation in the research will have no effect on his or her parole or pardon.

☐ **Confirmed**

2.5. [DETERMINATION] Protected populations. IRB approval is required for the use of the subject populations listed here. Check the boxes for any of these populations that will be purposefully included. (In other words, being a part of the populations is an inclusion criterion for the study.)

The WORKSHEETS describe the criteria for approval but do not need to be completed and should not be submitted.

Document Date & Version

06.29.2023

Version 4.6

APPLICATION IRB Protocol

Researcher Date & Version

mm/dd/yyyy

Version x.x

Page 9 of 55

Check all that apply	Population	Worksheet Name and Link
	Fetuses in utero	WORKSHEET Pregnant Women
	Neonates of uncertain viability	WORKSHEET Neonates
	Non-viable neonates	WORKSHEET Neonates
	Pregnant women	WORKSHEET Pregnant Women

2.5.a. If you check any of the boxes above, use this space to provide any information that may be relevant for the IRB to consider.

Click or tap here to enter text.

2.6. [DETERMINATION] Native Americans or non-U.S. indigenous populations. Will Native American or non-U.S. indigenous populations be actively recruited through a tribe, tribe-focused organization, or similar community-based organization?

Indigenous people are defined in international or national legislation as having a set of specific rights based on their historical ties to a particular territory and their cultural or historical distinctiveness from other populations that are often politically dominant.

Examples: a reservation school or health clinic; recruiting during a tribal community gathering.

☒ **No**

☐ **Yes** → Name the tribe, tribal-focused organization, or similar community-based organization. The UW IRB expects that tribal/indigenous approval will be obtained before beginning the research. This may or may not involve approval from a tribal IRB. The study team and any collaborators/investigators are also responsible for identifying any tribal laws that may affect the research.

Click or tap here to enter text.

2.7. [DETERMINATION] UW Medicine and UW Dentistry residents and fellows. Will the research involve UW Medicine or UW Dentistry residents or fellows as study subjects?

If it will → **(1)** Describe in the Recruiting section ([4.1](#)) and Risks section ([10.1](#)) how you will ensure that residents and fellows feel free to truly make a voluntary decision about participation (i.e., no negative consequences from supervisors for saying “no”) and how you will ensure that any research data will not be used in the residents’ and fellows’ supervisor or program evaluation of them; **AND**
(2) You must inform the UW HR Labor Relations representative who negotiates with the resident’s and fellows’ union about the study before beginning it. This is currently [name] [contact].

2.8. [DETERMINATION] Third party subjects. Will the research collect private identifiable information about individuals *other than* the study subjects? Common examples include: collecting medical history information or contact information about family members, friends, co-workers.

“Identifiable” means any direct or indirect identifier that, alone or in combination, would allow you or another member of the research team to readily identify the person. For example, suppose that the research is about immigration history. If subjects are

asked questions about their grandparents but are not asked for names or other information that would allow easy identification of the grandparents, then private identifiable information is not being collected about the grandparents and the grandparents are not subjects.

☒ **No**

☐ **Yes** → These individuals are considered human subjects in the study. Describe them and what data will be collected about them.

Click or tap here to enter text.

2.9. Number of subjects. Is it possible to predict or describe the maximum number of subjects (or subject units) needed to complete the study, for each subject group?

Subject units mean units within a group. For most research studies, a group will consist of individuals. However, the unit of interest in some research is not the individual. Examples:

- Dyads such as caregiver-and-Alzheimer's patient, or parent and child
- Families
- Other units, such as student-parent-teacher

Subject group means categories of subjects that are meaningful for the specific study. Some research has only one subject group – for example, all UW students taking Introductory Psychology. Some common ways in which subjects are grouped include:

- By intervention – for example, an intervention group, and a control group.
- By subject population or setting – for example, urban versus rural families
- By age – for example, children who are 6, 10, or 14 years old.

The IRB reviews the number of subjects in the context of risks and benefits. Unless otherwise specified if the IRB determines that the research involves no more than minimal risk: there are no restrictions on the total number of subjects that may be enrolled. If the research involves more than minimal risk: The number of enrolled subjects must be limited to the number described in this application. If it is necessary later to increase the number of subjects, submit a Modification. Exceeding the IRB-approved number ([over-enrollment](#)) will be considered non-compliance.

☐ **No** → Provide the rationale in the box below. Also, provide any other available information about the scope/size of the research. You do not need to complete the table.

Example: It may not be possible to predict the number of subjects who will complete an online survey advertised through Craigslist, but you can state that the survey will be posted for two weeks and the number who respond is the number who will be in the study.

Click or tap here to enter text.

☒ **Yes** → For each subject group, use the table below to provide the estimate of the maximum desired number of individuals (or other subject unit, such as families) who will complete the research.

Group name/description	Maximum desired number or individuals (or other subject unit) who will complete the research Provide numbers for the site(s) reviewed by the UW IRB and for the study-wide total number; example: 20/100
All patients who meet inclusion/exclusion criteria (single-arm study)	85

Group name/description	Maximum desired number or individuals (or other subject unit) who will complete the research Provide numbers for the site(s) reviewed by the UW IRB and for the study-wide total number; example: 20/100
Click or tap here to enter text.	Click or tap here to enter text.
Click or tap here to enter text.	Click or tap here to enter text.
Click or tap here to enter text.	Click or tap here to enter text.
Click or tap here to enter text.	Click or tap here to enter text.
Click or tap here to enter text.	Click or tap here to enter text.

